If you uploaded a separate research protocol document in the 'Research Protocol' page, cite the applicable section and page numbers from that document in the answer boxes below.

1 * Describe the purpose, specific aims, or objectives of this research. State the hypothesis to be tested:

Overall objectives: The specific research aims are to: 1) Establish the feasibility and acceptability of the SNF-PCC intervention by determining: (a) percentage of all SNF patients who meet eligibility criteria; (b) percentage of eligible patients who opt-out of participation; (c) percentage of participants who receive the SNF PCC and from whom all data are collected; (d) clinician fidelity to the standardized SNF-PCC protocol (defined as 90% adherence to protocol elements), and (e) participant/family caregiver satisfaction with the consult (acceptability), defined as ratings of 4 and 5 on the Consultation Satisfaction Questionnaire (1-5 scale; higher scores reflect greater satisfaction); 2) Estimate the effect size of the SNF-PCC intervention on participant/family caregiver reported quality of life at baseline and follow-up (between 14-21 days post baseline measurement) among 80 participants; and 3) Determine adherence to SNF-PCC recommendations at 15 days post SNF-PCC.

Primary outcome variable(s) Patient/Caregiver Quality of Life: Baseline, follow-up (14-21 days later) measured by the Palliative Outcomes Scale version 2 (POSv2), a 12 item survey that measures quality of life in five dimensions: 1) physical; 2) emotional; 3) psychological; 4) spiritual needs, and 5) provision of information and support. Items scored on a 5 point Likert Scale (0=not at all, 4= overwhelmingly) based on symptom/need in the past week. Overall profile score is calculated by summing responses to the 10 questions (range 0-40). Source: patient or family caregiver; Time to complete: 5-7 minutes.

Secondary outcome variable(s) 1) Palliative Care Consultation Satisfaction: within 15 days post-SNF-PCC; measured by Consultation

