Between 14 days and 21 days after the baseline POS is administered, all subjects will be asked to complete the POSv2 again virtually via telephone. The POS will be given a total of two times to those in the INTERVENTION and CONTROL groups; at baseline and follow up (14-21 days later). During this follow-up, subjects in the INTERVENTION ARM who receive a palliative care encounter will also be asked to complete the Consultation Satisfaction Questionnaire (CSQ) survey. The CSQ measures the INTERVENTION group satisfaction and therefore will only be given to INTERVENTION group at follow up. The CONTROL group WILL NOT receive a palliative care encounter therefore a consultation satisfaction questionnaire (CSQ) is NOT appropriate to administer.

Deidentified subject demographics will be collected on all participants in the following way: Research staff will review subject's medical records and enter de-identified data into REDCap (ACTS Staff assists with research team access to subject's medical record).

The goal of the intervention is to prevent, identify and treat symptoms early in the course of SNF care, establish goal directed treatment decisions, and support the patient and family in decision making. We anticipate that many Palliative care encounters involve a single encounter with the patient and/or surrogate decision maker, but we have made allowances for follow up visits depending on individual patient and family needs (e.g., symptom management, continuing goals of care discussions). We will use usual care as the control condition. Usual care consists of traditional resources focused on skilled nursing care without services to support specialty palliative care. A usual care comparison will test whether the Palliative Care Encounter improves patient/family reported outcomes compared to traditional services. We have chosen to not use an attention control condition because the goal of this pilot clinical trial is to assess feasibility and determine the effect size of the intervention on the primary outcome.

Research staff will collect measures via phone or through a secured online template to minimize missing data at two time points (baseline & 14-21 days later) during the study. All data will be entered and managed in a Research Electronic Data Capture (REDCap) database by the RA, project manager, or the PI.

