Patient/Caregiver Quality of Life: Baseline, follow-up (14-21 days later) measured by the Palliative Outcomes Scale version 2 (POSv2), a 12 item survey that measures quality of life in five dimensions: 1) physical; 2) emotional; 3) psychological; 4) spiritual needs, and 5) provision of information and support. (RESEARCH PROCEDURE)

Palliative Care Consultation Satisfaction: within 15 days post-SNF-PCC; measured by Consultation Satisfaction Questionnaire (CSQ). The CSQ is an 18 item patient/caregiver-report instrument that measures communication and satisfaction of a consult in four domains 1) general satisfaction, 2) professional care, 3) depth of relationship, 4) perceived length of consultation (scale format: 5-point Likert, strongly agree to strongly disagree) (RESEARCH PROCEDURE)

Palliative Care Encounter (STANDARD OF CARE)

Trained provider will discuss illness trajectories, establish and communicate patient-directed goals that guide health care decisions, identify and treat illness-related symptoms, and identify psycho-spiritual needs and approaches to mitigate suffering.

2 * Describe all procedures already being performed for diagnostic or treatment purposes (if not applicable to the study, enter "N/A"):

The Palliative Care encounter is Standard of Care.

3 * Describe the duration of an individual participant's participation in the study:

Up to 21 days.

4 * Describe the amount of time it will take to complete the entire study:

Entire project is 12 months in length.

5 * Describe any additional participant requirements:

N/A

Sample Size and Data Analysis

If you uploaded a separate research protocol document in the 'Research Protocol' page, cite the applicable section and page numbers from that document in the answer boxes below.

1 * Provide the rationale and sample size calculations for the proposed target population:
Sample Size and Power Calculations

The goal of Specific Aim 1 is to establish the feasibility of the post-acute Skilled Nursing Facility (SNF) Palliative Care (PC) intervention for patients with advanced serious illness. Following guidelines on sample size selection for pilot studies by Hertzog et al.,¹ 40 per group is adequate for establishing feasibility and acceptability of a pilot study.

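### Does timing the satisfaction questionnaire from the consult in one place and from baseline in another undermine the Aim 1 results?

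*Combined protocol and SAP*

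**What the plan says.** Justification, Objective, & Research Design item 1 lists consult satisfaction as a secondary outcome and times it from the consult. Study Procedures item 1 and Surveys/Questionnaires item 1 repeat this: "Palliative Care Consultation Satisfaction: within 15 days post-SNF-PCC".

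Study Procedures item 1 also describes how the CSQ is given. The follow-up contact is timed from baseline: "Between 14 days and 21 days after the baseline POS is administered, all subjects will be asked to complete the POSv2 again". Intervention participants who had an encounter complete the CSQ at that contact: "The CSQ measures the INTERVENTION group satisfaction and therefore will only be given to INTERVENTION group at follow up". In that sentence the restriction concerns the arm. But the same item names only two collection points, so the follow-up contact is the only CSQ occasion described.

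Two parts of Aim 1 use the result. Aim 1(c) is the "percentage of participants who receive the SNF PCC and from whom all data are collected". Aim 1(e) is "participant/family caregiver satisfaction with the consult (acceptability), defined as ratings of 4 and 5 on the Consultation Satisfaction Questionnaire". Neither carries a time condition.

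No visible section fixes the consult day relative to baseline. The stated goal is to "prevent, identify and treat symptoms early in the course of SNF care", and more than one encounter is possible: "we have made allowances for follow up visits depending on individual patient and family needs". Adherence has a similar wording difference. Aim 3 is to "Determine adherence to SNF-PCC recommendations at 15 days post SNF-PCC", while the secondary outcome list has it measured within that period, by medical record review.

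**The concern.** One questionnaire has one clock that starts at the consult and another that starts at baseline. After an early consult, staff can follow the contact window exactly and still obtain a CSQ more than 15 days after the consult. Earlier consults produce more such days, and the plan favours early care, so good delivery of the intervention could make late forms more common. The plan does not say how to treat a late form or which encounter starts the 15 days.

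The stake is Aim 1. If one analyst excluded late forms and another kept them, the same data would give different completion and acceptability figures. In a pilot whose first aim is feasibility and acceptability, that discretion would matter if the plan really left it open.

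**Working it through.** **Inputs.** Baseline is day 0. The contact day f runs from 14 to 21, which is 8 permitted days (Study Procedures item 1). The CSQ limit is 15 days after the consult (same item, and Surveys/Questionnaires item 1). The consult day d is not given; d of 0 or later is an assumption. The plan gives no figure of its own to reproduce here.

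**Late contact days.** A CSQ is late if f − d > 15. The number of late days among the 8 is max(0, 6 − d), and the longest overrun is 21 − d − 15 days.

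| Consult day d | Late contact days | Number late of 8 | Contact days meeting both limits |
|---|---|---|---|
| 0 | 16–21 | 6 | 2 |
| 1 | 17–21 | 5 | 3 |
| 2 | 18–21 | 4 | 4 |
| 3 | 19–21 | 3 | 5 |
| 4 | 20–21 | 2 | 6 |
| 5 | 21 | 1 | 7 |
| 6 to 14 | none | 0 | 8 |

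The largest overrun is 21 − 0 − 15 = 6 days. For consults on days 15 to 21, the contact must also follow the consult, which leaves 7 usable days at day 15 and 1 at day 21, none of them late. So every consult day from 0 to 21 has at least one contact day that satisfies both texts. The late count falls as d rises, so starting the clock from a later encounter can only reduce it; counting from the first encounter is the worst case.

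**Consult before baseline.** No visible section rules this out. At day −1, 7 of the 8 days are late; at day −2, all 8 are.

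**What exclusion would do.** Suppose all 40 intervention participants are consulted on the same day, contacts are spread evenly, and late forms are discarded. None of these three is stated in the plan.

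- Day 0: late forms 40 × 6/8 = 30, so Aim 1(c) could not exceed 10/40 = 25% of the arm.
- Day 3: late forms 40 × 3/8 = 15, so the ceiling is 25/40 = 62.5%.
- Day 6 or later: no late forms, so the ceiling is 100%.

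For Aim 1(e), assume 80% rate 4 or 5. The Wilson 95% interval is [p + z²/2n ± z√(p(1−p)/n + z²/4n²)] / (1 + z²/n) with p = 0.80 and z = 1.96. It gives 65.2–89.5% for n = 40, 60.9–91.1% for n = 25 and 49.0–94.3% for n = 10.

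**Whether the plan excludes late forms.** Aim 1(c) turns on whether data were collected, and a form completed on day 18 has been collected. Aim 1(e) turns on the rating. Sample Size and Data Analysis item 2 contains no timing exclusion. Keeping all forms, Aim 1(c) can reach 100% for every consult day in the table, and Aim 1(e) uses every completed form.

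**Adherence.** A check exactly 15 days after the consult falls on day d + 15, which passes day 21 once d is 7 or more. It is done by record review and needs no contact with the participant. The 21 days in Study Procedures item 3 describe an individual's participation and do not bar later chart review. The section on waiver of authorization keeps the linking key until data collection is complete.

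**The case for a change.** The strongest case for a change is that both texts are current and the day counts are exact. The CSQ feeds a leading aim of the pilot, and one sentence would remove any choice made after seeing the data. With an extreme set of consult days, the gap between enforcing and ignoring the limit is wide, from 25% to 100% on Aim 1(c).

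The inconsistency stands, as does the absence of a named index encounter. The large effect does not. It needs an exclusion rule that the plan does not contain, one shared consult day and an even spread of contacts. Forty is also an upper bound on the forms, since only participants who had an encounter are asked. Early care is described relative to the nursing facility stay, not to the baseline survey, so it does not place consults on days 0 to 5.

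The possible edits do not point one way either. Dropping the 15-day limit would lengthen the recall period for satisfaction; keeping it would mean scheduling the contact around the consult. Both are workable, and the choice is one of preference.

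**Conclusion.** No change to the plan follows. This is a wording inconsistency on a secondary outcome, with a gap that analysts will fill sensibly by counting every CSQ obtained at the follow-up contact. That is also the plain reading of Aim 1(c) and 1(e). The overrun is at most 6 days and arises only for consults on days 0 to 5; both limits can be met for any consult from day 0 to day 21. How many participants would be affected cannot be computed from the documents.

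This rests on the consult not preceding baseline. If it did, more contacts would be late, but the plan would still discard none of them. The two wordings for adherence are a clerical matter of the same kind. The primary POS comparison, with its common 14 to 21 day window in both arms, is untouched.

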A clinical trial is a research study in which one or more human subjects are prospectively assigned to one or more interventions (which may include placebo or other control) to evaluate the effects of those interventions on health-related biomedical or behavioral outcomes.

Yes No

ID: VIEW4E0280569E000
Name: v2_Type of Research

Lay Summary

- 1 * Provide a summary of the background and purpose of the study in language that can be understood by a person without a medical degree.

More than 30% of adults over age 65 receive care in nursing homes (NHs) under the Part A Medicare Skilled Nursing Facility (SNF) benefit in the last six months of life.¹ These patients often receive care that is focused on intense rehabilitation and/or aggressive, disease-modifying therapies with minimal consideration for palliative-oriented care.²⁻⁵ In addition to potential for poorer end-of-life (EOL) outcomes including undertreated pain and dyspnea, almost one quarter of SNF patients are rehospitalized,⁶ putting them at risk for medication errors, burdensome treatments, pressure ulcers, and higher mortality.⁷⁻⁹ Recent research suggests a significant association between NH palliative care consultation (PCC) and lower rates of hospitalization and emergency room visits; the association is even stronger for those receiving earlier PCC.^{10,11} Palliative care is patient and family centered care that incorporates symptom assessment and management and open communication and documentation of patients/families goals of care and preferences for treatments. The most widely used and studied model of palliative care in NHs is hospice; however, most patients receiving Medicare SNF benefits are not eligible for the Medicare Hospice benefit.¹² PCC is a promising option in this setting, particularly because it allows the concurrent use of rehabilitation and disease-modifying therapies; however, there is little research about the processes and outcomes of SNF PCC.¹³ Specifically, multi-component palliative care interventions have not been rigorously studied in controlled trials. Using published guidelines for designing and pilot testing complex interventions,^{14,15} this proposal aims to establish the feasibility and preliminary efficacy of a SNF PCC intervention for patients with advanced serious illness.

ID: VIEW4E02805CF7000
Name: v2_Lay Summary

Justification, Objective, & Research Design

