Page 10 of 18Satisfaction Questionnaire (CSQ). The CSQ is an 18 item patient/caregiver-report instrument that measures communication and satisfaction of a consult in four domains 1) general satisfaction, 2) professional care, 3) depth of relationship, 4) perceived length of consultation (scale format: 5-point Likert, strongly agree to strongly disagree). Source: patient or family caregiver; Time to complete: 3-5 minutes 2) Adherence to SNF-PCC recommendations: within 15 days post-SNF-PCC; measured by: medical record review.

2 * Discuss the research design including but not limited to such issues as: probability of group assignment, potential for subject to be randomized to placebo group, use of control subjects, etc.:

Pilot clinical trial with usual care control; 40 participants in each arm.

Aim 1 of this study is to establish the feasibility and acceptability of the SNF-PCC intervention.

Aim 2 of this study is to estimate the effect size of the SNF-PCC on the Palliative Outcomes Scale.

Aim 3 of this study is to determine overall adherence quantitatively as a percentage of all SNF-PCC recommendations that are implemented as well as adherence rates for specific recommendations.

3 * Describe the relevant prior experience and gaps in current knowledge. Describe any relevant preliminary data:

Palliative care is goal-directed, patient and family-centered care that focuses on a wide range of physical, psychosocial, and spiritual needs for persons with serious, life-limiting illnesses. Despite its association with improved quality of care, higher satisfaction, and better symptom management at the end of life, palliative care is not widely available to Medicare patients in the Skilled Nursing Facility (SNF) setting. We will test an evidence-based intervention derived from existing palliative care standards for adults over age 60 with life limiting illness who are admitted to a nursing home for SNF care.

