Specific Aim 2 of the study is to estimate an effect size for the SNF-PCC intervention on patient/family caregiver reported quality of life as measured by the Palliative Outcomes Scale, whose reported estimated standard deviation is approximately 6.1.2 As such, group sample sizes of 40 each produce a two-sided 80% confidence interval for the true mean measure of effect (difference in means) with a width of 3.4 units.

2 * Provide the plan for data analysis. Include in the description the types of comparisons that are planned (e.g., comparison of means, comparison of proportions, regressions, analysis of variance, etc.), which is the primary comparison/analysis, and how the analyses proposed will relate to the primary purposes of the study:

The primary analysis will be to compare the mean pre-post changes in the Palliative Outcomes Scale (POS) between the intervention and control arms. Linear regression models will be used to compare the two groups. The within-arm changes and differences between arms will be summarized with two-sided 90% CIs and p-values corresponding to tests against the null hypothesis of no (zero) change or difference. We will also explore subgroup effects of the intervention on endpoints by testing for statistical interactions between the binary group indicator and covariates of interest such as sex, age, and race.

Other key parameters needed to plan a follow-up study will be estimated as well, including the standard deviation (SD) and intraclass correlation coefficient (ICC) of each endpoint. The ICC summarizes the degree of correlation of values among patients within a site, which is an important parameter when planning a cluster randomized controlled trial.

*ID: VIEW4E02806052800
Name: v2_Sample Size and Data Analysis*

Sharing of Results

1 * Describe whether results (study results or individual subject results, such as results of investigational diagnostic tests, genetic tests, or incidental findings) will be shared with subjects or others (e.g., the subject's primary care physicians) and if so, describe how it will be shared:
N/A

ID: VIEW4E02808CBD800
Name: v2_Sharing of Results

Psychological/Behavioral/Educational Methods & Procedures

You indicated on the "Type of Research" page that your study involves a psychological/behavioral/educational method or procedure such as a survey, questionnaire, interview, or focus group.

1 * Select all behavioral methods and procedures which apply to this study:

- Surveys/questionnaires

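### The stated confidence-interval width of 3.4 units does not follow from its inputs, is given at 80% although the analysis reports 90% intervals, and counts every enrolled patient as a completer

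*Combined protocol and SAP*

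**What the plan says.** The only precision figure for the POS effect is in Sample Size and Data Analysis, item 1. Taking a POS standard deviation of about 6.1, it says that "group sample sizes of 40 each produce a two-sided 80% confidence interval". The full width of that interval, for the between-arm comparison of means, is put at 3.4 units.

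Item 2 of the same section defines the analysis: "The primary analysis will be to compare the mean pre-post changes in the Palliative Outcomes Scale (POS) between the intervention and control arms". Linear regression is used, and results are summarised with two-sided 90% intervals.

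The number enrolled equals the number in the width calculation. Justification, Objective, & Research Design, item 2, has "Pilot clinical trial with usual care control; 40 participants in each arm". Aim 2, in item 1 of that section, concerns quality of life "at baseline and follow-up (between 14-21 days post baseline measurement) among 80 participants". Participant Selection, item 2, gives a total enrolment of 80.

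Participants may withdraw at any time (Withdrawal of Participants, item 3), and residents or surrogates may decline any survey (Vulnerable Populations - Cognitively Impaired, item 2). The text supplied gives no expected non-completion rate.

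**The concern.** Estimating the effect size is Aim 2, and the estimates are meant to inform a follow-up study. In an estimation pilot, the interval width tells the reader what the trial can deliver. Three things undermine it here. The figure does not follow from its inputs. It is quoted at a lower confidence level than the one to be reported. It also rests on 40 analysable change scores per arm when 40 per arm is all that will be enrolled. A patient without the second POS has no change score and drops out of the comparison as described. A reader planning the next trial would therefore expect a tighter interval than the plan's own inputs support.

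**Working it through.** **Inputs.** SD 6.1, n = 40 per arm, 80% level, stated full width 3.4 (Sample Size and Data Analysis, item 1). 90% level (item 2). Losses of 10%, 20% and 25% are assumptions, because the documents give no rate.

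**Formula.** Full width = 2 × q × SD × √(1/n₁ + 1/n₂), where q is the normal or t quantile.

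**1. The plan's own figure.** The standard error is 6.1 × √(2/40) = 1.364.
- 80%, normal: 2 × 1.2816 × 1.364 = 3.50
- 80%, t with 78 df: 2 × 1.2925 × 1.364 = 3.53

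Neither rounds to 3.4; they exceed it by 2.8% and 3.7%. Rounding within 6.1 does not explain the gap: an SD of 6.05 gives 3.50 × 6.05/6.1 = 3.47 by the normal quantile. An SD of 6.0 would give 3.44, which is a possible source of the miss. At SD 6.1, a width of 3.4 needs 43 per arm.

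**2. The level the analysis will report.**
- 90%, normal: 2 × 1.6449 × 1.364 = 4.49
- 90%, t: 2 × 1.6646 × 1.364 = 4.54

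The change of level alone adds 4.54 − 3.53 = 1.01 units with nobody lost.

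**3. Fewer completers (t quantile, SD 6.1).**

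| Assumed loss | Completers per arm | 80% width | 90% width | Ratio to 40 per arm (80%) |
|---|---|---|---|---|
| 0% | 40 | 3.53 | 4.54 | 1.000 |
| 10% | 36 | 3.72 | 4.79 | 1.055 |
| 20% | 32 | 3.95 | 5.09 | 1.121 |
| 25% | 30 | 4.08 | 5.27 | 1.158 |

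Measured from the correct 3.53, a loss of 10-25% widens the 80% interval by about 5-16%, or 0.19 to 0.55 units. That is less than the effect of the change of level.

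**4. What the 6.1 refers to.** The plan does not say whether 6.1 is the SD of change or of a single POS score. If it is a single-time SD, and r is the correlation between baseline and follow-up, the SD of change is 6.1 × √(2(1 − r)). The two SDs coincide only at r = 0.5.

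| r | SD of change | 80% width, 40 per arm | 80% width, 32 per arm | 90% width, 40 per arm |
|---|---|---|---|---|
| 0.3 | 7.22 | 4.17 | 4.67 | 5.37 |
| 0.5 | 6.10 | 3.53 | 3.95 | 4.54 |
| 0.7 | 4.73 | 2.73 | 3.06 | 3.52 |

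This uncertainty moves the width more than the assumed losses do.

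**The case against.** The strongest reply is that this is a pilot. No powered test fails, and complete data collection is itself a feasibility outcome under Aim 1(c). The numerical miss is under 4%. That is fair as to scale, but a pilot whose second aim is estimation should still state its precision correctly and at the level it will report.

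A second reply is that the actual width could be 3.4 or less. If 6.1 is a single-time SD, 3.4 at the 80% level is still met with 20% loss when r is about 0.63 or higher. A regression that adjusted for baseline POS could also be tighter. This stands as a possibility, so a reader should not infer that the stated precision will certainly be missed. But the plan gives no correlation and does not name baseline POS as a covariate. At the 90% level with all 80 complete, 3.4 would need an SD of change of 6.1 × 3.4/4.54 = 4.57, that is r = 1 − (4.57/6.1)²/2 = 0.72.

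A reader might also go further and infer that many patients will be lost, more of them controls, so that the effect estimate is biased. The Lay Summary says "almost one quarter of SNF patients are rehospitalized" and links palliative consultation with "lower rates of hospitalization and emergency room visits". The documents do not support that inference. The rehospitalisation figure is background without a time window and is not a POS non-completion rate. Study Procedures, item 1, already plans telephone or online collection, and a surrogate may answer, so a hospitalised patient is not automatically missing. Unequal loss between arms, and any bias from it, is hypothetical. It would also hardly affect the width: with 64 completers, 36 versus 28 gives 3.98 at the 80% level, against 3.95 for 32 versus 32.

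**Conclusion.** The precision statement is wrong as written. With its own inputs the 80% width is 3.50 to 3.53, not 3.4. At the 90% level of the analysis plan it is 4.49 to 4.54 with no losses, about a third wider than the figure quoted (4.54/3.4 = 1.34). It also leaves no room for a missing follow-up score. With an assumed loss of 10-25%, the t-based width is 3.7-4.1 at 80% and 4.8-5.3 at 90%. All of these rest on 6.1 being the SD of change, which the plan leaves open. The confidence level and the meaning of the SD matter more than attrition within the range shown. The point concerns stated precision only and makes no finding of bias or of differential loss.

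**What to change.** In Sample Size and Data Analysis, item 1:

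1. Correct 3.4 to 3.5 for 40 per arm at the 80% level.
2. Restate the precision at the 90% level used in item 2: about 4.5 with 40 completers per arm.
3. Give that width for a stated range of completers, for example 30 to 40 per arm (5.3 to 4.5 at 90%, if 6.1 is the SD of change), and label the assumed non-completion rate as an assumption.
4. Say whether 6.1 is the SD of change or of a single score. If it is a single-time SD, give the assumed baseline to follow-up correlation and recompute.

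The cost is a few sentences and a less favourable stated precision. No added enrolment, visits or staff are needed.

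### Aim 2 precision is justified with an 80% confidence interval of width 3.4, but the plan reports 90% intervals, which are about 4.5 units wide on the same inputs

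*Combined protocol and SAP*

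**What the plan says.** All the relevant text is in the section Sample Size and Data Analysis.

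- **Item 1, Aim 1.** The sample size is supported by pilot-study guidance: "40 per group is adequate for establishing feasibility and acceptability of a pilot study".
- **Item 1, Aim 2.** The POS is given a standard deviation of about 6.1, taken from a cited source. With "group sample sizes of 40 each", the plan says the design will "produce a two-sided 80% confidence interval for the true mean measure of effect (difference in means) with a width of 3.4 units". There is no power calculation and no other numerical argument for this aim.
- **Item 2, analysis.** The primary analysis is to "compare the mean pre-post changes in the Palliative Outcomes Scale (POS) between the intervention and control arms" by linear regression. Reporting is then specified: "The within-arm changes and differences between arms will be summarized with two-sided 90% CIs and p-values".

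The 40-per-arm figure agrees with the design statement under Justification, Objective, & Research Design: "Pilot clinical trial with usual care control; 40 participants in each arm".

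**The concern.** Aim 2 is an estimation aim, so the expected width of the confidence interval is its design criterion. The width offered belongs to an 80% interval, whereas the interval to be reported is a 90% one. Both refer to the between-arm difference on the same scale, and the plan neither explains the change of level nor gives a width at 90%. A reader would take 3.4 units as the precision of the reported result, but the planned interval is wider on the same inputs.

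A second gap bears on the same number. The SD of 6.1 is attributed to the scale, while the primary analysis compares pre-post changes. A single-score SD and a change-score SD are generally different, and the plan does not say which one 6.1 is.

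What is at stake is how well the pilot is understood to pin down the effect size. The validity of the analysis and the number enrolled are not in question.

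**Working it through.** **Inputs, all from Sample Size and Data Analysis:** SD 6.1; 40 per arm; two-sided 80% level (item 1); two-sided 90% level (item 2).

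**Formula.** Full width = 2 × quantile × SE, with SE = SD × √(1/n₁ + 1/n₂).

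SE = 6.1 × √(2/40) = 1.364.

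**Step 1: the plan's own figure (80%).**
- Normal: 2 × 1.2816 × 1.364 = 3.496
- t, 78 df: 2 × 1.2925 × 1.364 = 3.526

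The printed value is 3.4. The results are 2.8% (normal) and 3.7% (t) above it, and both round to 3.5. Rounding of the SD does not account for this: 6.05 still gives 3.47 (normal). An exact 3.4 needs an SD of about 5.93 (normal). Reading 3.4 as a half-width does not work either, since it would correspond to a confidence level of about 98.7%. The printed figure is therefore a full width at 80%, slightly low.

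**Step 2: the planned interval (90%), same inputs.**
- Normal: 2 × 1.6449 × 1.364 = 4.487
- t, 78 df: 2 × 1.6646 × 1.364 = 4.541

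The total width is about 4.5 and the half-width about 2.2 to 2.3.

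**Step 3: size of the gap.**
- Effect of the level alone: 4.487 / 3.496 = 1.283 (normal); 4.541 / 3.526 = 1.288 (t)
- Against the printed figure: 4.487 / 3.4 = 1.320 (normal); 4.541 / 3.4 = 1.336 (t)

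**Step 4: what if 6.1 is a single-score SD?** The pre-post correlation r is not in the plan, so the values below are assumptions. They also assume equal SDs at the two time points. The change SD is 6.1 × √(2(1 − r)). If the regression also adjusts for baseline, which the plan does not state, the residual SD is 6.1 × √(1 − r²). Widths are at 90%, using t with 78 df.

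| Assumed r | Change SD | Width, unadjusted change | Width, baseline-adjusted |
|---|---|---|---|
| 0.3 | 7.22 | 5.37 | 4.33 |
| 0.5 | 6.10 | 4.54 | 3.93 |
| 0.7 | 4.73 | 3.52 | 3.24 |

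The figure of 4.5 therefore applies if 6.1 is the SD of change or, for an unadjusted change analysis, if r is about 0.5.

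**Step 5: evaluable numbers.** All widths above assume that all 40 per arm have follow-up. As an illustration only, 30 evaluable per arm with SD 6.1 gives SE = 6.1 × √(2/30) = 1.575 and a 90% width of 5.18 (normal) or 5.27 (t).

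**The case against.** The strongest reply is that nothing printed is mislabelled. Item 1 says plainly that its interval is 80%, and a team may plan at one level and report at another. That is true, but the plan does not say it is doing so and gives no width for the interval it will report. If the difference is deliberate, one sentence with the 90% width settles it.

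A second reply is that 4.5 is itself uncertain. The natural reading of 6.1 is the SD of the scale score, and on that reading the 90% width depends on an unstated correlation. From the formulas in the working, a 90% width of 3.4 requires an analysed SD of 3.4 / (2 × 1.6646 × √(2/40)) = 4.57. That corresponds to r of about 0.72 for unadjusted change or about 0.66 with baseline adjustment. This stands as a limit on the claim: the wider interval is a consequence of the plan's stated inputs, not a certainty about the data. It is also a reason to name the SD.

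A third reply is that this is a pilot, that no go/no-go rule or margin depends on 3.4, and that Aim 1 has its own justification for 40 per group. All of that is correct, and it keeps the point modest. It does not remove it, because width is the only numerical support given for Aim 2.

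Finally, 3.4 against 3.5 is a small slip, and the main point does not depend on it.

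**Conclusion.** The concern holds. The precision stated for Aim 2 is that of an 80% interval, while the plan will report a 90% interval. With SD 6.1 and 40 evaluable per arm, the reported interval would be about 4.5 units wide, not 3.4. About 28–29% of extra width comes from the change of level; the rest of the gap is the slightly low printed figure.

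The 4.5 rests on two assumptions: that 6.1 is the SD of the analysed change, and that follow-up is complete. If 6.1 is a single-score SD, assumed correlations of 0.3 to 0.7 put the 90% width between about 5.4 and 3.5 for unadjusted change, or between about 4.3 and 3.2 with baseline adjustment. The inconsistency between the two confidence levels does not depend on any of these assumptions. It should be corrected, although the point estimate, the primary analysis and the enrolment target are unaffected.

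**What to change.** Use one confidence level in items 1 and 2 and give the width that goes with it.

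- **If 90% is kept**, item 1 could read:

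> With 40 evaluable participants per arm, and assuming 6.1 is the standard deviation of the pre-post change, the two-sided 90% confidence interval for the between-arm difference has a total width of about 4.5 units (half-width about 2.3).

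- **If 80% is intended throughout**, change item 2 to 80% and print 3.5 in place of 3.4.
- **If the two levels are meant to differ**, say so, give the reason, and print both widths.

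In each case, state whether 6.1 is a single-score or a change-score SD. If it is a single-score SD, state the assumed pre-post correlation and whether the regression adjusts for baseline, and compute the width accordingly. State that the width assumes complete follow-up, and label any width at a smaller evaluable number as an assumption.

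The cost is one or two sentences. On the stated inputs the quoted precision becomes less favourable if 90% is kept. No change to enrolment, data collection or the primary analysis is requested.
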